7.3.3 FOLLOW-UP

Visit 2, Week 1

Subjects will return to the clinic one week (± 3 days) after the first treatment. Adverse events and any changes to concomitant medications will be recorded.

Subjects will receive treatment of the face as described above in section 7.3.2. Following treatment, the investigator will examine the treated area and report the immediate response.

The assessment of discomfort/pain will be based on the subject's completion of the 100 mm VAS immediately after treatment.

Subjects will be discharged from the clinic and will be instructed to return for the Visit 3, Week 2 assessment and treatment.

Visit 3, Week 2

Subjects will return to the clinic one week (± 3 days) after the last treatment. Adverse events and any changes to concomitant medications will be recorded.

Subjects will receive treatment of the face as described above in section 7.3.2. Following treatment, the investigator will examine the treated area and report the immediate response.

The assessment of discomfort/pain will be based on the subject's completion of the 100 mm VAS immediately after treatment.

Subjects will be discharged from the clinic and will be instructed to return for the Visit 4, Week 3 assessment and treatment.

Visit 4, Week 3

Subjects will return to the clinic one week (± 3 days) after the last treatment. Adverse events and any changes to concomitant medications will be recorded.

Subjects will receive treatment of the face as described above in section 7.3.2. Following treatment, the investigator will examine the treated area and report immediate response.

The assessment of discomfort/pain will be based on the subject's completion of the 100 mm VAS immediately after treatment.

Subjects will be discharged from the clinic and will be instructed to return for the Visit 5, Week 4 assessment and treatment.

Visit 5, Week 4

Subjects will return to the clinic one week (± 3 days) after the last treatment. Adverse events and any changes to concomitant medications will be recorded. Photographs will be taken as described above in section 7.3.2. Subjects will complete a 5-point Likert satisfaction scale.

Subjects will receive treatment of the face as described above in section 7.3.2. Following treatment, the investigator will examine the treated area and report immediate response.

The assessment of discomfort/pain will be based on the subject's completion of the 100 mm VAS immediately after treatment.

Subjects will be discharged from the clinic and will be instructed to return for the Visit 6, Week 5 assessment and treatment.

Visit 6, Week 5

Subjects will return to the clinic one week (± 3 days) after the last treatment. Adverse events and any changes to concomitant medications will be recorded.

Subjects will receive treatment of the face as described above in section 7.3.2. Following treatment, the investigator will examine the treated area and report immediate response.

The assessment of discomfort/pain will be based on the subject's completion of the 100 mm VAS immediately after treatment.

Subjects will be discharged from the clinic and will be instructed to return for the Visit 7, Week 6 assessment and treatment.

Visit 7, Week 6

Subjects will return to the clinic one week (± 3 days) after the last treatment. Adverse events and any changes to concomitant medications will be recorded.

Subjects will receive treatment of the face as described above in section 7.3.2. Following treatment, the investigator will examine the treated area and report immediate response.

The assessment of discomfort/pain will be based on the subject's completion of the 100 mm VAS immediately after treatment.

Subjects will be discharged from the clinic and will be instructed to return for the Visit 8, Week 7 assessment and treatment.

Visit 8, Week 7

Subjects will return to the clinic one week (± 3 days) after the last treatment. Adverse events and any changes to concomitant medications will be recorded. Photographs will be taken as described above in section 7.3.2. Cutometer® measurements of the treated area will be obtained.

Subjects will receive treatment of the face as described above in section 7.3.2. Following treatment, the investigator will examine the treated area and report immediate response.

The assessment of discomfort/pain will be based on the subject's completion of the 100 mm VAS immediately after treatment.

Subjects will complete the GAIS scale and the 5-point Likert satisfaction scale.

Subjects will be discharged from the clinic and will be instructed to return for the final study visit, Visit 9, Week 20 assessment.

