2.3 POTENTIAL RISKS AND BENEFITS

2.3.1 KNOWN POTENTIAL RISKS

The potential risks for adverse effects of the treatment procedure include but are not limited to temporary swelling, redness, pain and burns at treatment site. The following long range risks were also identified as low probability adverse events: scarring, skin breakdown and hyper or hypopigmentation.

Previous studies have shown the immediate risks outlined above are transient and generally well-tolerated by patients. The long-range risks outlined above are theoretical, as there have been no reports of these incidences.

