7.3.4 FINAL STUDY VISIT

Visit 9, Week 20

Subjects will return to the clinic twelve weeks (± 2 weeks) after the last treatment for the final visit. Adverse events and any changes to concomitant medications will be recorded. Photographs will be taken as described above in section 7.3.2. The subject will complete the GAIS scale and the 5-point Likert satisfaction scale. Cutometer® measurements of the treated area will be taken.

The termination form will be completed and subjects will be discharged from the clinic and terminated from the study. The PI will record all reportable events with start dates occurring any time after informed consent is obtained until 7 (for non-serious AEs) or 30 days (for SAEs) after the last day of study participation.

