10.5 SAMPLE SIZE

The PI has used G*Power 3.10.10 software⁴ to generate *a priori* minimal sample size calculations for the primary study endpoint: changes in *gross elasticity* (GE) repeated measure face measurement in a sample of consented eligible women at three time points: a) prior to RF/PEMF, b) at time of RF/PEMF completion, and c) three months after treatment completion.

These calculations indicate that a minimal sample size of approximately **45** patients would easily afford at least a 0.804784 $1 - \beta$ level of statistical power to detect statistically significant RF/PEMF sample subgroup measurement differences observing a coefficient Alpha of 0.05 two-tailed level of significance. This sample size is based on both a conservative 0.3 (i.e., *Medium*) Effect Size for RF/PEMF treatment and pre-post procedure Cutometer[®] face gross elasticity measurement differences reported in Krueger, et. al (2011).⁵

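### As written, the week 7 GAIS and satisfaction forms follow the eighth treatment, while week 4 satisfaction and week 7 R2 precede that day's treatment, and 10.5 places the second R2 reading at completion

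*Combined protocol and SAP*

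**What the plan says.** Three visits matter, all in section 7.3 of the combined protocol and SAP.

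- **Visit 5, week 4.** Measurements are listed first: "Photographs will be taken as described above in section 7.3.2. Subjects will complete a 5-point Likert satisfaction scale". The treatment paragraph follows.
- **Visit 8, week 7.** The text opens in the same way: "Photographs will be taken as described above in section 7.3.2. Cutometer® measurements of the treated area will be obtained". Treatment is next: "Subjects will receive treatment of the face as described above in section 7.3.2. Following treatment, the investigator will examine the treated area". The pain VAS comes after it, then "Subjects will complete the GAIS scale and the 5-point Likert satisfaction scale", then discharge.
- **Visit 9, week 20.** No treatment is given: "Subjects will return to the clinic twelve weeks (± 2 weeks) after the last treatment for the final visit".

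The schedule of events (7.3.7) marks procedures by visit and gives no order within a visit. Section 10.4.3 makes GAIS and satisfaction repeated measures. Section 10.5 names three time points for gross elasticity, the second being "b) at time of RF/PEMF completion". Section 2.3.1 lists among the potential risks "temporary swelling, redness, pain and burns at treatment site" and describes the immediate ones as transient. Section 7.3.2 has erythema and edema assessed straight after each session.

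**The concern.** Subjects rate their own facial appearance (GAIS) and their satisfaction with facial laxity. If the week 7 forms are filled in after the session, the subject may be judging a face that is still red or swollen. The week 4 satisfaction form would not carry that influence, and neither would anything at week 20. A change in score across visits then combines any lasting effect with the acute response. The study has no control arm and subjects are not blinded, so nothing in the design separates the two.

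The second strand is exposure. One visit label, week 7, would cover an R2 reading after seven sessions and subject ratings after eight. Section 10.4.1 speaks of three elasticity measurements per patient, so the week 7 R2 enters that model. Anyone relying on section 10.5 would take it for an end-of-course value.

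**Working it through.** **1. The plan's own figure.** Section 10.5 states a power of 0.804784 for N = 45, effect size 0.3 and two-sided alpha 0.05. It cannot be uniquely reproduced, because the test, the correlation and the sphericity assumption are not given. For example, a paired t test with a standardized change of 0.3 gives 0.503. A three-measure within-subject F test with f = 0.3 and an assumed correlation of 0.5 gives 0.994. The point made here does not depend on this figure, since the order of assessments changes none of these values.

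**2. Exposure at each assessment.** Treatments are given at Visits 1 to 8 (weeks 0 to 7), eight in all. Counting in written order:

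| Assessment | Treatments received | Time since last treatment |
|---|---|---|
| Week 4 satisfaction | 4 of 8 | about 1 week (± 3 days) |
| Week 7 R2 and photographs | 7 of 8 | about 1 week (± 3 days) |
| Week 7 GAIS and satisfaction | 8 of 8 | same day |
| Week 20 R2, GAIS, satisfaction | 8 of 8 | 12 weeks (± 2 weeks) |

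Satisfaction (weeks 4, 7, 20) therefore has three different relations to the last session. GAIS (weeks 7, 20) has two: same day and 12 weeks.

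**3. Which reading is time point (b).** Sections 7.1.1 and 7.3.7 allow Cutometer readings only at baseline, week 7 and week 20. Section 10.5 lists before treatment, at completion, and three months after completion. Matching the two lists, (b) can only be the week 7 reading. That reading is written before the eighth session, so it reflects 7/8 = 87.5% of the course.

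**4. What an acute shift could do (assumed sizes).** The documents give neither the shift nor the SD of change. Take a one-sample t test of within-subject change, n = 45, df = 44, two-sided 0.05, critical value 2.015. With a net shift of d SD and no lasting change, the noncentrality is d × √45:

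- d = 0.1: 0.1 × 6.708 = 0.671, probability of significance 0.101
- d = 0.2: 0.2 × 6.708 = 1.342, probability 0.259
- d = 0.3: 0.3 × 6.708 = 2.012, probability 0.503

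For scale, d = 0.2 arises if a net 20% of subjects move one grade in the same direction and the SD of change is one grade (0.20 × 1 / 1 = 0.2). With no shift the probability is 0.05.

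**The case against.** The best reply is that the order is only the order of writing. No sentence says the week 7 forms are completed after treatment. The words about timing attach to the VAS, and the two forms stand in their own paragraph. This is right, and a reader should not infer that the ratings are shown to be made minutes after the session. What stands is that the visit text otherwise runs chronologically, from arrival to discharge. Staff who follow it would give the form before treatment at week 4 and after it at week 7, and nothing else in the protocol fixes the order.

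Four stronger readings are tempting and are not supported:

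- **That both scales mix pre-session and post-session ratings.** GAIS is not given at week 4, so it has no pre-session rating. That mix applies to satisfaction alone.
- **That 26% is the plan's false-positive rate.** It follows from one assumed shift and from a t test that the plan does not specify for these ordinal scales. Section 2.3.1 names swelling and redness as potential risks; it does not say that every session produces them or which way ratings would move.
- **That the main result is compromised.** Section 4.2.1 defines the primary endpoint on baseline and the final measurement. Week 20 ratings are taken with no session that day. Section 4.2.2 keeps week 7 photographs out of the efficacy rating. Taking R2 before the session also protects it from the acute response.
- **That post-intervention is wrong for week 7 only.** The synopsis and section 3 use it for weeks 4, 7 and 20 alike.

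It can also be said that the label in 10.5 is a wording matter, since Visit 8 is the visit at which treatment finishes. That is a fair limit on its weight, but the reading is still one session short of the full course.

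**Conclusion.** The point holds at low to modest severity. The written sequence is inconsistent between Visits 5 and 8. If it is followed, the week 7 subject ratings are taken when an acute skin response is possible, and the week 4 and week 20 ratings are not. The week 7 R2 follows 7 of 8 treatments and is not a reading at completion.

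This rests on two inferences: that staff follow the order of the text, and that time point (b) in section 10.5 is week 7, a term that section does not use. The size of any bias in the ratings is unknown. The 10% to 50% range illustrates assumed net shifts of 0.1 to 0.3 SD and is not an estimate. Interpretation of week 7 GAIS and satisfaction, and of the middle point in the three-point elasticity model, is affected. The contrast of baseline with the final visit and the week 20 ratings are not.

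**What to change.** 1. In section 7.3.3, Visit 8, move GAIS and the Likert scale ahead of that day's treatment, next to photographs and Cutometer. Say in words that they are completed before treatment. This matches the Likert scale at Visit 5, where the same words should be added.
2. In section 10.5, describe time point (b) as week 7, after 7 of 8 treatments.
3. In the synopsis and section 3, express weeks 4, 7 and 20 as weeks from baseline in place of weeks post-intervention.

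The cost is the order of two forms at one visit plus some wording. No procedure is added and the treatment schedule does not change. The downside is that no subject rating would follow the full course until week 20. If the sponsor prefers to keep the week 7 forms after treatment, the protocol should say so and the report should present them as same-day post-session ratings.

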7.3.4 FINAL STUDY VISIT

Visit 9, Week 20

Subjects will return to the clinic twelve weeks (± 2 weeks) after the last treatment for the final visit. Adverse events and any changes to concomitant medications will be recorded. Photographs will be taken as described above in section 7.3.2. The subject will complete the GAIS scale and the 5-point Likert satisfaction scale. Cutometer® measurements of the treated area will be taken.

The termination form will be completed and subjects will be discharged from the clinic and terminated from the study. The PI will record all reportable events with start dates occurring any time after informed consent is obtained until 7 (for non-serious AEs) or 30 days (for SAEs) after the last day of study participation.

7.3.5 EARLY TERMINATION VISIT

Subjects who terminate the study early for whatever reason, will be asked to return to the clinic, if they are willing, to complete the final visit (Visit 9). Adverse events and the reason for early termination will be recorded.

7.3.6 UNSCHEDULED VISIT

Participants will be encouraged to contact the PI at any time during the course of the study if they believe they are experiencing an AE or undesirable outcome. If necessary, an unscheduled visit will be made to examine the participant and provide further care as needed. If an unscheduled visit occurs, the

reason for the unscheduled visit will be documented. If the unscheduled visit is the result of an adverse event, the event will be recorded on the adverse event CRF.

7.3.7 SCHEDULE OF EVENTS TABLE

Procedures	Screening (Visit 1, Week 0)	Baseline (Visit 1, Week 0)	Follow-up (Visit 2, Week 1)	Follow-up (Visit 3, Week 2)	Follow-up (Visit 4, Week 3)	Follow-up (Visit 5, Week 4)	Follow-up (Visit 6, Week 5)	Follow-up (Visit 7, Week 6)	Follow-up (Visit 8, Week 7)	Final Study Visit (Visit 9, Week 20)
Informed Consent	X									
Eligibility assessment	X	X								
Demographics	X									
Medical History	X									
Physical exam	X									
Photographic imaging		X				X			X	X
Cutometer® readings		X							X	X
Administer treatment		X	X	X	X	X	X	X	X	
Immediate response		X	X	X	X	X	X	X	X	
Subject pain VAS		X	X	X	X	X	X	X	X	
Subject GAIS									X	X
Subject satisfaction						X			X	X
Adverse events		X	X	X	X	X	X	X	X	X
Concomitant medications		X	X	X	X	X	X	X	X	X

7.4 JUSTIFICATION FOR SENSITIVE PROCEDURES

Not applicable

7.5 CONCOMITANT MEDICATIONS, TREATMENTS, AND PROCEDURES

All concomitant prescription medications taken during study participation will be recorded on the case report forms (CRFs). For this protocol, a prescription medication is defined as a medication that can be

prescribed only by a properly authorized/licensed clinician. Medications to be reported in the CRF are concomitant prescription medications, over-the-counter medications and non-prescription medications.

7.5.1 PRECAUTIONARY MEDICATIONS, TREATMENTS, AND PROCEDURES

Not applicable

7.6 PROHIBITED MEDICATIONS, TREATMENTS, AND PROCEDURES

Treatment with any invasive or non-invasive cosmetic procedure to the face and neck (other than the investigative treatment) during the study period will not be permitted.

7.7 PROPHYLACTIC MEDICATIONS, TREATMENTS, AND PROCEDURES

Medical grade glycerin will be applied to the treated area.

7.8 RESCUE MEDICATIONS, TREATMENTS, AND PROCEDURES

In the event that the subject experiences pain, the principal investigator may prescribe any analgesic deemed appropriate to the level of pain. If a subject experiences any first, second or third degree burn or pain beyond narcotics, then the following procedure will be implemented:

- Immediate triage and treatment of the patient shall be determined by the treating physician and based upon severity and type of burn identified.
- Event will be reported to the study Director within 24 hours of occurrence. If the event meets the criteria of a SAE, then it must be reported on the SAE form.
- Copy of the patient chart and treatment parameters are to be forwarded to the study Director within 24 hours.
- Study Director will be responsible for issuing a written report to the company and the IRB Chairman no later than 7 days from the incident.
- Long term follow-up and care shall continue at the discretion of the treating physician.

All patients experiencing a complication of the device will be followed a minimum of 2 years following the initial injury. Longer care and observation will be at the discretion of the treating physician.

All minor complications such as appearance or altered sensation, except for pain, can be reported within 30 days of patient complaint. Both chart and treatment parameters are to be provided to the study Director and shared with the company and IRB chairman.

7.9 PARTICIPANT ACCESS TO STUDY AGENT AT STUDY CLOSURE

At study closure, participants will be given a list of providers in the area who can continue treatments to the same area or other body areas if desired. However, subjects will be notified that additional treatments will incur a cost not covered by the study.

8 ASSESSMENT OF SAFETY

8.1 SPECIFICATION OF SAFETY PARAMETERS

In addition to spontaneous reports of adverse events, subjects will complete a 100 mm pain VAS and the principal investigator will examine the treated area and report immediate response.

8.1.1 DEFINITION OF ADVERSE EVENTS (AE)

Adverse event means any untoward medical occurrence associated with the use of an intervention in humans, whether or not considered intervention-related (21 CFR 312.32 (a)).

8.1.2 DEFINITION OF SERIOUS ADVERSE EVENTS (SAE)

An AE or suspected adverse reaction is considered "serious" if, in the view of either the investigator or sponsor, it results in any of the following outcomes: death, a life-threatening adverse event, inpatient hospitalization or prolongation of existing hospitalization, a persistent or significant incapacity or substantial disruption of the ability to conduct normal life functions, or a congenital anomaly/birth defect. Important medical events that may not result in death, be life-threatening, or require hospitalization may be considered serious when, based upon appropriate medical judgment, they may jeopardize the patient or subject and may require medical or surgical intervention to prevent one of the outcomes listed in this definition. Examples of such medical events include allergic bronchospasm requiring intensive treatment in an emergency room or at home, blood dyscrasias or convulsions that do not result in inpatient hospitalization, or the development of drug dependency or drug abuse.

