8.1.3 DEFINITION OF UNANTICIPATED PROBLEMS (UP)

This definition could include an unanticipated adverse device effect, any serious adverse effect on health or safety or any life-threatening problem or death caused by, or associated with, a device, if that effect, problem, or death was not previously identified in nature, severity, or degree of incidence in the investigational plan or application (including a supplementary plan or application), or any other unanticipated serious problem associated with a device that relates to the rights, safety, or welfare of subjects (21 CFR 812.3(s)).

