8.5 STUDY HALTING RULES

The study may be halted at any time by the sponsor, the IRB, Health Canada or the FDA due to safety concerns. Examples of findings that might trigger a safety review are the number of SAEs overall, the number of occurrences of a particular type of SAE, severe AEs/reactions, or increased frequency of events. If the study is halted, the sponsor will immediately notify all investigational sites, the IRB(s) and the applicable regulatory authority.

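### The serious-event definition in 8.1.2 has no outcome for permanent bodily damage, so the lasting injuries this device plan names would generally not be classed, expedited or tabulated as serious

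*Combined protocol and SAP*

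**What the plan says.** Section 8.1.2 makes an event serious, in the view of the investigator or the sponsor, if it results in death, a threat to life, hospital admission or a longer stay, "a persistent or significant incapacity or substantial disruption of the ability to conduct normal life functions, or a congenital anomaly/birth defect". A further clause allows important medical events to be considered serious when, on medical judgment, they may jeopardize the subject and "may require medical or surgical intervention to prevent one of the outcomes listed in this definition". The examples given are bronchospasm, "blood dyscrasias or convulsions that do not result in inpatient hospitalization, or the development of drug dependency or drug abuse".

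The harms expected from the device are of another kind. Section 2.3.1 states: "The following long range risks were also identified as low probability adverse events: scarring, skin breakdown and hyper or hypopigmentation". Section 8.2.3 lists scarring, pigment change and loss of hair in the treated area among the expected events.

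Seriousness then controls several routes. Section 8.4.2 requires every serious event to reach the sponsor within 24 hours, whatever its expectedness or relation to the device. Section 8.3 (repeated in 7.3.4) collects non-serious events for 7 days and serious events for 30 days after participation ends. Section 8.5 says: "Examples of findings that might trigger a safety review are the number of SAEs overall, the number of occurrences of a particular type of SAE", and continues with other triggers. Section 10.4.4 promises a table of serious treatment-emergent events and of events leading to discontinuation.

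**The concern.** The definition is built for drug reactions, while the plausible lasting harm here is local injury to facial skin. If the definition cannot take in that kind of injury, the study's count of serious events says little about the harm that matters most for a cosmetic device. At stake are the speed of notice to the sponsor, the length of collection after a subject leaves, and whether lasting injuries appear in the one safety table that the plan commits to for serious events.

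**Working it through.** No arithmetic is needed to establish the point; it turns on how the sections fit together. Take as test case a permanent facial scar or pigment change, managed as an outpatient and first noticed at the week 20 visit.

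1. **Listed outcomes (8.1.2).** The subject has not died, her life was not threatened, she was not admitted, and there is no birth defect. Incapacity or disruption of normal life functions would not ordinarily be met by a scar that does not limit activity. No listed outcome applies.

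2. **Important-medical-event clause (8.1.2).** It is discretionary, and it covers an event that "may require medical or surgical intervention to prevent one of the outcomes listed in this definition". Treating the scar prevents none of the listed outcomes. The clause extends the list to averted cases; it does not add a new kind of outcome. Result: generally not serious.

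3. **24-hour report (8.4.2).** Expectedness and relatedness play no part there, so listing scarring as expected in 8.2.3 does not close this route. The definition alone does. The test case misses it.

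4. **Collection window (8.3, 7.3.4).** Non-serious events are collected to day 7 and serious ones to day 30 after participation ends, a difference of 30 − 7 = 23 days. For a woman who completes, the final visit is already 12 weeks (± 2 weeks) after the last treatment, so this matters little. It matters for a woman who leaves soon after a treatment and does not return for the visit that 5.4.2 and 7.3.5 ask for: a lasting injury starting on days 8 to 30 need not be recorded if it is classed as non-serious.

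5. **Safety review (8.5).** Two of the examples count SAEs, and the test case enters neither. Severity is not a dependable substitute. Section 8.2.1 grades by need for treatment and interference with daily activity, so a permanent scar needing little treatment can be graded mild and miss the severe-reaction example too. The last example in 8.5, a rise in event frequency, does not depend on seriousness or severity and stays open.

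6. **Table (10.4.4).** A scar found at week 20, after all eight treatments, leads to no discontinuation and is not serious. It falls in neither tabulated group.

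7. **Unanticipated device effects (8.1.3).** This section has its own wording, beginning "any serious adverse effect on health or safety or any life-threatening problem or death caused by, or associated with, a device", and does not refer to 8.1.2. It also requires that the effect was not already identified in the plan in nature, severity or incidence. Scarring, skin breakdown, pigment change and hair loss are identified in 2.3.1 or 8.2.3, so they would usually fail that second test under any SAE definition. Seriousness decides only when the severity or incidence exceeds what was identified.

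8. **Routes that do not need seriousness.** Section 7.8 sends any burn to the study director within 24 hours and to the company and IRB chairman within 7 days. It gives minor complications of appearance or sensation a 30-day limit from the complaint, with chart and treatment parameters shared with the company and IRB chairman. It follows device complications for at least 2 years. Section 8.3 requires all adverse events to be documented and followed, and 10.4.4 requires all of them to be recorded and reported.

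**The case against.** The strongest reply is that nothing is hidden. A scar would be recorded with its severity, relationship, outcome and duration (10.4.4), listed by participant (10.4.10), followed to resolution or stabilization (8.3) and, as a complication of appearance, passed to the company and IRB chairman under 7.8. A cluster could prompt a review through the frequency example in 8.5. Section 8.1.2 also leaves seriousness to judgment, so an investigator could call a disfiguring scar a substantial disruption of normal life. All of this stands, and it limits the point to classification, timing and tabulation.

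A reader might infer more: that permanent scarring would go unreported, or that the gap in 8.1.2 is what keeps these injuries out of the unanticipated-device-effect reports in 8.4.2 and 8.4.3. The documents support neither. The first is answered by 7.8, 8.3 and 10.4.4. On the second, 8.1.3 has its own definition, and injuries already named in the plan are mostly excluded because they are already identified.

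The reply does not remove the remaining gap. Discretion is not a criterion, and the 7.8 route sharpens the problem: a lasting facial scar could be handled as a minor appearance complaint with a 30-day limit. The late scar or pigment change also has no counterpart to the 24-hour route for burns.

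**Conclusion.** The point holds for the SAE definition and what hangs directly on it. As written, 8.1.2 would generally leave the lasting injuries named in the plan outside the 24-hour SAE report, the 30-day collection window, the SAE-count examples in 8.5 and the serious-event table. A study with permanently scarred participants could therefore state that no serious adverse events occurred while still listing the scars as adverse events.

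The size is qualitative. The documents give no rate for these injuries, and 2.3.1 says "The long-range risks outlined above are theoretical, as there have been no reports of these incidences", so no expected count can be derived. The conclusion assumes that investigators apply the listed outcomes at face value and that the injury is managed without admission. It does not rest on the text of the standards cited in Sections 11 and 13.1, which the documents do not reproduce. The primary endpoint and its analysis are unaffected. This is a cheap improvement to safety reporting, not a flaw in the efficacy conclusion.

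**What to change.** 1. Add to the outcomes in 8.1.2: *permanent damage to a body structure (including permanent scarring, pigment change or disfigurement of the treated area) or permanent impairment of a body function, or medical or surgical intervention to prevent it*.
2. State that the investigator or the sponsor judges permanence, and that the 24-hour clock in 8.4.2 starts at that judgment. Without this the clock has no clear start for an injury seen about 12 weeks after the last treatment.
3. Replace the drug-type examples in 8.1.2 with device-relevant ones, and update the SAE form.
4. Reconcile 8.1.2 with 7.8, so that the same lasting injury does not fall under both a 24-hour serious-event report and a 30-day route for minor appearance complications.
5. Reconcile 2.3.1, which calls the long-range risks theoretical and unreported, with 8.2.3, which lists scarring and pigment change under a definition of expected reactions as common and known for the device.

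The wording in 8.4.2 (SAE report), 8.3, 8.5 and 10.4.4 then needs no change. The unanticipated-device-effect route would still generally not apply to these injuries. The cost is a short amendment and a few more events reported as serious; treatment, sample size and efficacy analysis stay as they are.
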